### **7.2 Subject Disposition**

The number of subjects screened for the study, failing screening (with breakdown by reason), number of subjects entering the run-in period, number of subjects discontinued during the run-in period (with break-down by reason for discontinuation) will be presented.

The number of subjects randomized in the double-blind period of the study, included in the safety, intent to treat, modified intent to treat, per protocol populations, prematurely discontinued from the study (along with the reasons for discontinuation) will be presented by treatment. Number of subjects enrolled by center will be tabulated for all randomized subjects, safety, mITT and PP populations.

### **7.3 Inclusion/Exclusion criteria**

Number and percentage of subjects violating each inclusion/exclusion criterion will be presented by criterion. This analysis will be based on all screened subjects.

Violation of inclusion/exclusion criteria will be listed.

#### **7.4 Diagnosis of Osteoarthritis according to ACR Criteria**

Number and percentage of subjects answering Yes to the following CRF questions will be presented by treatment for the safety population:

- Is the subject having knee pain?
- Did the Subject meet at least 3 of the following 6 criteria for the target knee?
  - Age > 50 years
  - Stiffness < 30 minutes
  - Presence of crepitus
  - Bony tenderness
  - Bony enlargement
  - No Palpable warmth

Kellgren-Lawrence grade will also be summarized descriptively, presenting the number and percentage of subjects with each grade (0 to 4).

All details of the osteoarthritis diagnosis collected on the CRF will be listed.

#### **7.5 Joint examination**

Results of joint examination will be summarized descriptively for each question asked at the Joint Examination CRF page. Results also will be listed.

#### **7.6 Demographic and Baseline Characteristics**

Demographic characteristics will include:

- age
- gender
- race
- ethnicity.

Baseline characteristics include:

- height
- weight
- body mass index (BMI)
- Baseline POM VAS target knee pain score

- Baseline WOMAC Pain Subscale score.

Descriptive statistics will be presented for age (years), BMI, VAS and WOMAC scores. Frequency counts and percentage will be presented for sex, race, ethnicity. BMI will be reported in kg/m^2.

Age will be derived from Informed Consent Signed Date (INFCSD) and Date of Birth (DOB) as the number of whole years between those two dates.

Demographic and baseline characteristics will be evaluated for comparability across treatment groups in the following manner. Continuous variables (age, BMI, VAS and WOMAC scores) will be analyzed with an analysis of variance with factors of treatment and investigational center. Overall p-value for the global null hypothesis of all groups being equal will be displayed. Categorical variables (gender, ethnicity, race) will be analyzed with a Cochran-Mantel-Haenszel general association test, stratified by investigational center.

These analyses will be performed for the ITT, Safety, mITT and PP populations.

Demographic and baseline characteristics will be presented in the by-subject listings.

## **7.7 Medical History**

Medical history will be recorded at Visit 1 Screening. Reported terms will be coded using MedDRA dictionary version 20.0.

Medical history will be summarized by MedDRA system organ class and preferred term for the safety population.

## **7.8 Prior and Concomitant Medication**

Prior and concomitant medications will be assessed at screening and at each subsequent study visit. Medications will be coded using WHO Drug Dictionary version Sep-2016 B2.

Medication will be classified as prior, if the end date is known and is prior to the first use of the study medication (any study medication, including run-in). Medications that are ongoing or ended after the first use of the study medication will be classified as concomitant. If the end date of the medication is unknown, it will also be considered concomitant. If the end date is partially known, the medication will be considered concomitant, unless the known part of the end date

rules out the possibility that the medication could have ended after the start of the study drug. Please see [appendix 11.3](#) for more details on handling of partial dates.

Prior and concomitant medications will be separately summarized by ATC class (the highest available level) and preferred name for the safety population.

The prior and concomitant medications will be listed in a by-subject listing.

## 7.9 Protocol Deviations

Protocol deviations will be derived algorithmically and additionally reported by study centers according to the MYL-1601N-3002 Protocol Deviations Guidance Document. Eventually all approved protocol deviations will be entered in the Protocol Deviations eCRF page.

Subjects with protocol deviations deemed to have an impact on treatment evaluation will be excluded from the Per Protocol population. The list of protocol deviations which lead to exclusion of subjects from the PP population will be finalized at the Blind Data Review (BDR) meeting to be held prior to database lock.

Major deviations that have an impact on treatment evaluation may include:

- Violation of inclusion/exclusion criteria
- Use of prohibited medications
- Missing WOMAC Pain Subscale assessments
- Final visit out of window
- Missing visits
- Violation of rescue medication use rules
- IP compliance <75% or >125%
- Administration of incorrect or expired IP

Protocol deviations will be summarized by deviation category and treatment group. This analysis will be performed for all randomized subjects.

## 7.10 Handling of Missing Data

For demographic and baseline characteristics, each variable will be analyzed using all available data. Subjects with missing data will be excluded only from analyses for which data are not

available. For efficacy analysis, patients who discontinued the study early will be included in the ITT and mITT analysis with LOCF approach; subjects who discontinue the study due to lack of treatment effect will also be included in the PP analysis with LOCF approach.

For WOMAC pain total score, the following imputation method will be used for handling missing values. If one item is missing, the missing value will be imputed by averaging remaining 4 items and total score will be calculated using sum of 5 items. If more than one items are missing, then the total pain score will be assigned to missing value at that visit. The LOCF method will be used for endpoint analysis if Visit 5 value is missing.

## **7.11 Efficacy Analyses**

All efficacy analyses will be based on the randomized treatment group as determined by the randomization schedule.

### **7.11.1 Center pooling**

To eliminate potential effect of random fluctuations at small center on the efficacy endpoints small centers will be pooled. A study center will be pooled if it doesn't meet both of the following conditions:

- It has at least 10 patients in the Per Protocol population;
- It has at least one patient in each treatment group in the Per Protocol population.

The smallest center that does not meet the above requirements will be pooled with the next smallest center. The procedure will be repeated until all pooled centers meet the above two requirements.

Pooled center will be used in all efficacy analyses.

### **7.11.2 Analyses of Primary Endpoint**

At all post-screening visits the subjects will complete the WOMAC Osteoarthritis Pain Subscale Ratings for the target (most severe) knee. The Pain Subscale score will be reported on the eCRF.

Missing Week 4 assessments will be imputed as follows. In the ITT and mITT analysis, if a subject discontinued from the study prior to Week 4 or misses the Week 4 assessment for any

other reason, the LOCF rule will be used to impute the score (the change in the score from the baseline visit to the last completed visit prior to discontinuation will be carried forward). In the Per Protocol analysis, if a subject discontinued from the study prior to Week 4 due to treatment failure, the LOCF rule will be used to impute the score (the change in the score from the baseline visit to the last completed visit prior to discontinuation due to treatment failure will be carried forward). If a subject is missing the Week 4 assessment for any other reason, the subject will be excluded from Per Protocol population.

The baseline score will be defined as the results from the latest exam prior to the start of study drug applications. For each post-baseline visit the change from baseline in the WOMAC Pain Subscale score will be calculated. The baseline value, time point value and change from baseline to the timepoint will be analyzed using descriptive statistics and will be tabulated by center, visit and treatment group. This summary will also be prepared for the subset of subjects with baseline WOMAC Pain Subscale score  $\leq 10$ .

Mean WOMAC Pain Subscale score will also be plotted graphically by visit with +/- SD bars. A separate line will be plotted for each treatment group.

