7.7 Subject withdrawal Criteria

Subjects will be discontinued from the study for any of the following reasons:

- If the subject withdraws his or her consent for any reason.
- If the subject's condition has worsened to the degree that the investigator feels, it is unsafe for the subject to continue in the study.
- If the subject's drug code is unblinded.
- If an adverse event occurs for which the subject desires to discontinue treatment or the investigator determines that it is in the subject's best interest to be discontinued.
- If the subject with a score of ≥ 20 mm on a 0-100 mm Visual Analog Scale (VAS) for the contralateral knee
- If there is a significant protocol violation.
- If the subject is lost to follow-up. (The investigator will document all attempts to reach the subject by telephone and/or in person in source documents before considering that subject lost to follow-up.)
- If the female subject becomes pregnant.
- Treatment failure based on investigator's discretion.

- Administrative reasons.

The reasons for a subject being discontinued will be documented in the source notes and captured in case report form.

If a subject is discontinued from the study for any reason, the Day 28/ Early Termination Visit procedures should be completed and any outstanding data and study drug should be collected. Data, in addition to the reason for discontinuation and the date of removal, will be captured on the End of Study section of eCRF.

In the event that a subject discontinues from the study at any time due to an adverse event, the reason for discontinuation, the nature of the event and its clinical course must be fully documented. For such a subject, the investigator must strive to follow the subject until the adverse event has resolved, become clinically insignificant, is stabilized, or the subject is lost to follow-up.

Should a serious adverse event be noted, procedures stated in [Section 11.2.2](#) must be followed.

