10.3.3 Visit 5: End of Study (Week 4/Day 28 ± 4)/Early Termination Visit

The following procedures will be performed.

- **Physical Examination and Vital Signs**
- **Serum Pregnancy Test (for all females of childbearing potential)**
- **Laboratory investigations**
- **ECG**
- **Pain on Movement (POM) assessment in both the knees- 100mm VAS**
- **WOMAC pain score assessment of the target knee**
- **Subject diary (treatment period) review and its collection**
- **Assessment of treatment compliance**
- **Collection of the unused IPs and rescue medication**
- **Application site reaction assessment Collection of unused medications (IP/NIMPs)**
- **Assess Adverse Events**
- **Assessment of Concomitant Medications**

Note:

- ⇒ Additional assessments could be performed as per Investigators' discretion during the study.
- ⇒ All the subjects will be instructed to apply the gel next day (Day 1) onwards.
- ⇒ Telephone contact: Principal investigator or designee will contact the subjects approximately midway between the visit 3-4 and visit 4-5 for assessment of the well-being, adverse event, concomitant medication, and treatment compliance. Additional telephonic contact will be done

to remind the subject regarding stoppage of rescue medication usage prior to scheduled visits (Visit 4, and Visit 5). The same will be documented in the source notes.

⇒ In case subject extends run-in period beyond 11 days, continuation of the subject will be decided in consultation with Medical monitor.

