### **7.11.3            Analyses of Secondary Endpoint Outcomes**

The following secondary endpoints will be evaluated in the same way as the primary endpoint, but will be considered as supportive information.

- The change from baseline to Week 2 in total WOMAC Pain Subscale score for the Target Knee.
- The change from baseline to Week 4 in total WOMAC Pain Subscale score for the Target Knee for the subgroup of subjects whose baseline WOMAC pain score is less than or equal to 10.
- The change from baseline to Week 4 in POM VAS score for the Target Knee.

Missing Week 2 assessments will be imputed as follows. In the ITT and mITT analysis, the LOCF rule will be used to impute the score, i.e. the change in the score from the baseline visit to the Early Termination visit, provided it occurs after baseline and within 18 days, (2 weeks + 4 days allowed window) will be carried forward. In the Per Protocol analysis, if a subject

discontinued from the study prior to Week 2 due to treatment failure, the LOCF rule will be used to impute the score as for ITT and mITT analyses. If a subject is missing the Week 2 assessment for any other reason, the subject will be excluded from Per Protocol analysis.

In the analysis of secondary endpoints a 95% CI for the Test/Reference ratio will also be presented in addition to 90% CI.

A descriptive summary by visit will also be created for POM VAS score.

Mean POM VAS score will also be plotted graphically by visit with Mean +/- SD error bars. A separate line will be plotted for each treatment group.

The following secondary endpoints will be summarized descriptively by treatment group:

- Number of days of acetaminophen (paracetamol) consumption during the trial.
- Average daily dose of acetaminophen (paracetamol) during the trial
- Total dose (mg) of acetaminophen (paracetamol) during the trial
- Percentage of patients that used acetaminophen (paracetamol) at least once during the trial

When calculating these endpoints, only days from the day of the first application of the randomized study drug to the day of the last application of the randomized study drug will be counted.

Number of days with any acetaminophen consumption will be counted from the subject's diary.

Average daily dose of acetaminophen will be calculated as follows:

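### SAP 7.11.2 and SAP 7.10 disagree on whether an Early Termination WOMAC score counts as the last observation for the Week 4 primary endpoint

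*SAP*

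**What the plan says.** Four places bear on the Week 4 value of a subject who stops early.

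- **SAP 7.11.2 (primary endpoint).** For ITT and mITT, "the change in the score from the baseline visit to the last completed visit prior to discontinuation will be carried forward". For treatment failures in the PP population the wording is parallel: the change to the "last completed visit prior to discontinuation due to treatment failure will be carried forward".
- **SAP 7.10 (missing data).** "The LOCF method will be used for endpoint analysis if Visit 5 value is missing". SAP 3.1 defines Visit 5 as the end-of-study or early termination visit.
- **SAP 7.11.3 (secondary endpoints).** For a missing Week 2 score, LOCF means "the change in the score from the baseline visit to the Early Termination visit, provided it occurs after baseline and within 18 days". Here the Early Termination score is itself the carried value.
- **Protocol 7.7 and 10.3.3.** "If a subject is discontinued from the study for any reason, the Day 28/ Early Termination Visit procedures should be completed", and the procedure list for that visit includes "WOMAC pain score assessment of the target knee".

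The protocol (12.2.2, 12.2.3 and 12.3.2) asks for LOCF without naming the source visit. SAP section 8 declares no departure from the protocol's analyses.

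**The concern.** Protocol 7.7 places the Early Termination assessment after the subject is discontinued. A rule that carries the last visit completed before discontinuation therefore passes over that score and falls back on Week 2, or on baseline if the subject stopped before Week 2. SAP 7.10 leads to the opposite result, because an Early Termination score fills the Visit 5 slot and leaves nothing to impute.

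These are two stated rules for the same primary outcome, so a programmer would have to choose between them. The choice affects mITT superiority for Test and for Reference and, to a lesser degree, PP equivalence. SAP 7.1.2 requires all three tests to succeed.

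The literal rule also sits awkwardly with SAP 6.5. A subject whose only post-baseline WOMAC comes from the Early Termination visit enters the mITT population because of that score. Under 7.11.2 the score is then set aside and the subject gets a change of 0.

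**Working it through.** **Plan figures.** No figure in the plan is in dispute here. As background, 363 / (1 − 0.10) = 403.3, rounded up to 404 per arm, and 3 × 404 = 1212, as stated.

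**The two Week 4 rules applied to one subject (assumed scores).**

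| Subject | SAP 7.11.2, literal | SAP 7.10 with Visit 5 = Early Termination |
|---|---|---|
| Baseline 12, Week 2 = 7, Early Termination on Day 20 = 11 | 7 − 12 = −5 | 11 − 12 = −1 |
| Baseline 12, no Week 2 visit, Early Termination on Day 10 = 11 | baseline carried: 0 | 11 − 12 = −1 |

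In the first row the literal rule gives the better outcome, in the second the worse one. For the second subject, SAP 7.11.3 would also use −1 as the Week 2 value.

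**Who is affected in the PP population.** SAP 6.6 requires 75% to 125% of scheduled applications, and SAP 7.12.2 sets the plan at 112. The minimum is 0.75 × 112 = 84 applications, or 84 / 4 = 21 days at four a day. Read literally, treatment failures before about Day 21 are outside PP, and a visit from Day 24 is already inside the Week 4 window. Both subjects in the table would be in mITT but not in PP.

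**Illustrative size, superiority.** Inputs from SAP 3.2: mean reductions 5.85 (SD 4.23) on active and 4.68 (SD 4.89) on placebo, a difference of 1.17. Assumptions: a share f of each arm stops early as failures, and the Early Termination score is D points worse than the carried score. The literal rule raises an arm's apparent reduction by f × D, so the active-placebo difference falls by (f_placebo − f_active) × D.

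| f active / f placebo | D = 1 | D = 2 | D = 4 |
|---|---|---|---|
| 2% / 4% | 0.02 | 0.04 | 0.08 |
| 3% / 6% | 0.03 | 0.06 | 0.12 |
| 5% / 10% | 0.05 | 0.10 | 0.20 |
| 5% / 5% | 0 | 0 | 0 |

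The non-zero entries run from 0.02 / 1.17 = 1.7% to 0.20 / 1.17 = 17.1% of the planned difference. If D is negative, the sign reverses.

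**Power per comparison.** SE = √((4.23² + 4.89²) / n), and power = Φ(difference / SE − 1.96).

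| n per arm | SE | 1.17 | 1.15 (smallest loss) | 0.97 (largest loss) |
|---|---|---|---|---|
| 363 | 0.339 | 93.2% | 92.3% | 81.6% |
| 404 | 0.322 | 95.3% | 94.7% | 85.4% |

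LOCF retains early discontinuations that have a post-baseline score, so 363, the number left after removing the dropout allowance, is too low a base for this calculation. The largest case also spends the whole 10% allowance on treatment failures in the placebo arm.

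**Illustrative size, equivalence.** Suppose the ratio is 1.00 under the literal rule. With Early Termination scores it becomes (5.85 − f_T × D) / (5.85 − f_R × D). With 10% failures on Test and 5% on Reference:

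- D = 1: 5.75 / 5.80 = 0.991
- D = 2: 5.65 / 5.75 = 0.983
- D = 4: 5.45 / 5.65 = 0.965

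With equal shares it stays at 1.00. These shares are generous for PP, where only late failures remain.

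**The case against.** The best defence is that the SAP as a whole points towards keeping the Early Termination score. Visit 5 includes that visit, 7.10 imputes only when Visit 5 is missing, 7.11.3 calls carrying that score LOCF, and 6.5 brings early discontinuers into mITT using LOCF. Discontinuation in 7.11.2 could also mean study exit, which the Early Termination visit closes. That is a reasonable account of what was intended. It does not settle the matter, because 7.11.2 is the specific rule for the primary endpoint and its wording, set beside Protocol 7.7, says otherwise.

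Other limits stand in full:

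- 7.11.3 governs Week 2 only. The conflict over the primary endpoint is between 7.11.2 and 7.10.
- Not every discontinued subject will have an Early Termination WOMAC. Protocol 7.7 says that "the Day 28/ Early Termination Visit procedures should be completed", but its list of reasons includes loss to follow-up and withdrawal of consent.
- A reader might infer that treatment failures always keep an earlier and better score. The documents do not support this. Protocol 10.4 links failure to a worsened condition, but 7.7 leaves it to the investigator's discretion and 12.2.3 speaks of lack of effect. Where baseline is carried, any improvement by Early Termination makes the literal rule the harsher one.
- If scores do worsen and failures are commoner on placebo, the effect on superiority is conservative: a loss of power, not a false positive.

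**Conclusion.** The point holds as an unresolved conflict within the SAP. Sections 7.11.2 and 7.10 can assign different Week 4 changes to the same early discontinuation. The mITT superiority analysis is the most exposed. PP equivalence is less so, because the 84-application minimum, read literally, leaves only late treatment failures.

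A reader might go further and say that the SAP has settled on discarding measured data. Section 7.10 prevents that conclusion.

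Direction and size cannot be determined from the documents, which give neither failure rates by arm nor Early Termination scores. The loss of 0.02 to 0.20 points from a planned 1.17 assumes failure shares of 2% to 5% on active, twice that on placebo, and a score gap of 1 to 4 points. If rates and gaps are equal across arms, the difference is unaffected. The case for acting rests on the need for one pre-specified primary outcome per subject, not on these figures.

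**What to change.** In SAP 7.11.2, replace the bracketed text for ITT, mITT and PP treatment failures with: *the change from baseline to the last available post-baseline WOMAC pain score, including the Early Termination visit, will be carried forward*. This also covers a subject who misses Week 4 without discontinuing, for whom the present wording has no reference point.

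SAP 6.4 puts every randomized subject in the ITT population, so add that ITT subjects with no post-baseline score have baseline carried, giving a change of 0. Align SAP 7.10 with the new sentence. Leave the 18-day limit on the Week 2 rule in 7.11.3 as it is; without it, a later score could fill a missing Week 2 value.

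The cost is two sentences in 7.11.2 and a matching edit in 7.10, using data already planned for collection. Finalise the change before unblinding.

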#### **7.11.2.1 Analysis of clinical equivalence of test and reference treatments**

To show the clinical equivalence, estimates of LS mean change from baseline to Week 4 in the WOMAC Pain Subscale score will be calculated for the test and reference treatment, and then the 90% CI for the LS mean ratio will be constructed using Fieller's method. Bioequivalence will be established if the 90% confidence interval for the ratio of test/reference LS means is contained within the interval [0.80, 1.25].

To this end, first an ANCOVA model will be fit with change from baseline to Week 4 in the WOMAC Pain Subscale score as outcome, baseline WOMAC Pain Subscale score as covariate and treatment, center and treatment-by-center interaction as factors on the data from test and reference treatments only (excluding Placebo subjects):

$$Y_{ijk} = b + a \cdot B_{ijk} + T_i + C_j + TCI_{ij} + \varepsilon_{ijk}$$

Where

- $Y_{ijk}$  is the change from baseline to Week 4 in WOMAC Pain Subscale score for the  $k$ th subject in the  $j$ th center with  $i$ th treatment
- $b$  is model intercept
- $B_{ijk}$  is the baseline WOMAC Pain Subscale score for the  $k$ th subject in the  $j$ th center with  $i$ th treatment
- $a$  is the model parameter associated with baseline WOMAC Pain Subscale score
- $T_i$  is the effect of the  $i$ th treatment
- $C_j$  is the effect of the  $j$ th center
- $TCI_{ij}$  is the interaction effect of the  $i$ th treatment and the  $j$ th center
- $\varepsilon_{ijk}$  is the random error (normally distributed with zero expected value)

If the treatment-by-center interaction factor is not significant at the 0.05 level, the model will be rerun without the interaction term. Treatment LS means and standard errors will be estimated from this model. Then Fieller's formula will be applied; covariance between treatment means will be assumed to be 0. See [appendix 11.2](#) for complete description of Fieller's formula.

Equivalence will be illustrated graphically by a plot including a vertical line corresponding to the 90% CI around the Test/Reference ratio with the ratio itself indicated by a dot with reference lines for 80% and 125%.

Analysis of bioequivalence will be performed primarily on the Per Protocol population, and additionally on the ITT and mITT populations as a sensitivity analysis.

